**Definition of Adverse Event and Serious Adverse Event**

**Adverse Event (AE)** means any untoward medical occurrence associated with the use of an intervention in humans, whether or not considered intervention-related (21 CFR 312.32 (a)). An event constitutes a disease, a set of related signs or symptoms, or a single sign or symptom.

**Serious Adverse Event (SAE):** A serious adverse event (SAE) for this population is an adverse event that:

- results in death; or
- is life-threatening (the patient was, in the view of the site investigator, in immediate danger of death from the event as it occurred); or
- requires inpatient hospitalization or prolongs an existing hospitalization; or
- results in persistent or significant disability or incapacity; or
- results in congenital anomaly/birth defect; or
- any other event that, based upon appropriate medical judgment, may jeopardize the subject's health and may require medical or surgical intervention to prevent one of the other outcomes listed in these definitions.

Classification of an Adverse Event (Relatedness, Severity, and Expectedness)

**Relatedness:** The suspected relationship between study interventions and any adverse event will be determined by the site investigator using the criteria below. Relatedness must be assessed by an investigator and may not be assessed by a research coordinator.

**A Phase I/II Randomized, Double-Blinded Standard of Care (Corticosteroid vs Sterile Amniotic Fluid for Osteoarthritis**

**PI: [name].**

**Version: 5.00 dated 23MAY2023**

- **Not Related:** The event is clearly related to other factors, such as the subject's clinical state, therapeutic interventions, or concomitant drugs administered to the subject.
- **Possibly Related:** The event follows compatible temporal sequence from the time of beginning the assigned study intervention, but could have been produced by other factors such as the subject's clinical state, therapeutic interventions, or concomitant drugs administered to the subject.
- **Probably Related:** The event follows a reasonable temporal sequence from the time of beginning the assigned study intervention, and cannot be reasonably explained by other factors such as the subject's clinical state, therapeutic interventions, or concomitant drugs administered to the subject.

**Severity:** The severity, which is a measure of intensity, of clinical adverse events and laboratory abnormalities will be recorded by the site investigator and categorized. The following guidelines will be used to describe severity.

- **Mild:** The event requires minimal or no treatment and does not interfere with the participants daily activities.
- **Moderate:** The event results in a low level of inconvenience or concern with the therapeutic measures. Moderate events may cause some interference with functioning.
- **Severe:** The event interrupts a participant's usual daily activity and may require systemic drug therapy or other treatment. Severe events are usually potentially life-threatening or incapacitating. Of note, the term "severe" does not necessarily equate to "serious".

**Expectedness of the Event:** All adverse events, including serious adverse events, will be evaluated as to whether their occurrence was expected or unexpected. An AE will be considered unexpected if the nature, severity, or frequency of the event is not consistent with the risk information described for the study intervention.

- **Expected:** An event is considered expected if it is known to be associated with the underlying condition or is related to the study intervention and is mentioned in the protocol, informed consent, or other study documents. An event may be expected despite the study subject's clinical state immediately prior to the event.

Expected adverse events for this study are:

- Pain at injection site
  - Swelling or effusion at injection site
  - Soreness
  - Bleeding at the injection site
- **Unexpected:** An event is considered unexpected if there are no prior data linking this event

**A Phase I/II Randomized, Double-Blinded Standard of Care (Corticosteroid vs Sterile Amniotic Fluid for Osteoarthritis**

**PI: [name].**

**Version: 5.00 dated 23MAY2023**

with either the condition or intervention under study or an event that occurred unexpectedly in the course of treatment.

**Treatment or Action Taken:** For each adverse event, the site investigator will record whether an intervention was required:

- Medical or surgical procedure
- Concomitant medication: started, changed, or discontinued
- Other, specify
- No action taken

**Outcome of Event:** Finally, the site investigator will record the clinical outcome of each adverse event as follows:

- Death
- Recovered and the patient returned to baseline status
- Recovered with permanent sequelae
- Symptoms persist

**Time Period for Adverse Events**

For purposes of this study, events that occur following randomization through the last follow-up visit at 12 months will be reported as adverse events. Serious adverse events, unexpected medically attended events, and new onset chronic illnesses will be recorded from randomization through twelve months after the last study dose. Specifically, events that occur following informed consent to participate in the study, but prior to actual randomization, are not adverse events. These should be recorded as baseline conditions.

**Data Collection Procedures for Adverse Events**

After patient randomization all adverse events (including serious adverse events) will be recorded according to relatedness, severity, and expectedness, as well as their duration and any treatment prescribed. Any medical condition present at the time of randomization, recorded in the patient's baseline history at study entry, which remains unchanged or improves (unless the clinician feels it is clinically relevant), will not be recorded as an adverse event at subsequent evaluations. However, worsening of a medical condition that was present at the time of randomization will be considered a new adverse event and reported.

Adverse events will be coded using the MedDRA coding vocabulary. Coding will be done centrally at the Data Coordinating Center as this requires specific training.

**Unanticipated Problems (UP)**

Unanticipated problems (UP) are defined as incidents, experiences, or outcomes that are unexpected, related or possibly to participation in the study, and suggest that the research places subjects at a greater risk of harm than was previously known or recognized. The site investigator will report unanticipated problems to the Data Coordinating Center within 24 hours of becoming aware of the event. A detailed completed report will be required to be sent to the Data Coordinating Center within 3

**A Phase I/II Randomized, Double-Blinded Standard of Care (Corticosteroid vs Sterile Amniotic Fluid for Osteoarthritis**

**PI: [name].**

**Version: 5.00 dated 23MAY2023**

working days of the event. After receipt of the complete report, the Data Coordinating Center will review these unanticipated problems to determine if there is a safety concern. In accordance with local IRB requirements, the site investigator may be required to report such unanticipated problems to the IRB in addition to notifying the Data Coordinating Center. The CTRM, medical monitor or DSMB may be notified of these events. In the event that the medical monitor believes that such an event warrants emergent suspension of enrollment in the trial, and DSMB staff cannot be reached expeditiously, the Data Coordinating Center will notify the study investigator ([name]) and all site investigators to cease enrollment in the trial. Resumption of enrollment will not occur without consent by the DSMB.

**Amendments**

Any amendments or administrative changes to an IRB approved protocol will not be initiated without submission of an amendment for IRB review and approval. Any amendments to the protocol that significantly affect the safety of subjects, the scope of the investigation, or the scientific quality of the study are required to submit the amendment for FDA review.

**Monitoring Serious Adverse Events and IND Safety reports**

A qualified physician will be designated to fulfill the function of the medical monitor for this study. Site investigators and/or research coordinators will report serious adverse events to the Data Coordinating Center within 24 hours of becoming aware of the event. A detailed completed report will be required to be sent to the Data Coordinating Center within 3 working days of the event, and the medical monitor will assess all serious adverse events reported from site investigators.

For each of these serious adverse events, the site investigator will provide sufficient medical history and clinical details for a safety assessment to be made with regard to continuation of the trial. The medical monitor will sign off on each SAE report after review. All SAE reports will be retained at the Data Coordinating Center, and all SAE reports will be available for review by DSMB members. The SAE reporting process may be incorporated into the Electronic Data Capture (EDC) System in use for the study.

In the unlikely event that the medical monitor believes an unexpected and study- related SAE warrants emergent cessation of enrollment in the trial, the DSMB chairperson will be immediately consulted. If this individual concurs with the judgment of the medical monitor, or if the DSMB chairperson cannot be reached expeditiously, the Data Coordinating Center will notify the study investigator ([name]), the CTRM, and all site investigators to cease enrollment in the trial. Resumption of enrollment will not occur without consent by the DSMB.

In accordance with local IRB requirements, the site investigator may be required to report such events to the IRB in addition to notifying the Data Coordinating Center.

After notification of the CTRM, and the DSMB chairperson, of serious, unexpected, and study-related adverse events or unanticipated problems (UP), decisions will be made whether to continue the study without change, and whether to convene the entire DSMB for an emergent meeting. If a decision is made to suspend enrollment in the trial, this will be reported to the study investigator ([name]), who will be instructed to report this to their local IRB.

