**STUDY STOPPING/ DISCONTINUATION**

Events used to trigger discontinuation or stopping of the study pending a safety investigation include:

- If there is one death, irrespective of attribution
- If there is a SAE, that is possibly or probably related to study drug injection (pAf or steroid injection)
- Signs of severe hypersensitivity in a least 10% of enrolled patients
- If there is one case of hypersensitivity, defined as an acute inflammatory reaction requiring invasive intervention
- If there an adverse event that is classified as Severe per protocol that is possibly or probably related to the IP Injection (AF or steroid)

In the event study enrollment has been suspended due to the above criteria or any other reason the FDA, the DSMB, IRB and the Sponsor must be notified. Enrollment and treatment will be resumed after a review of the incident and of any corrective and preventive actions have been established with consultation between the study team, the Sponsor, and the DMSB. The study may not resume without FDA approval.

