**A Phase I/II Randomized, Double-Blinded Standard of Care (Corticosteroid vs Sterile Amniotic Fluid for Osteoarthritis**

**PI: [name].**

**Version: 5.00 dated 23MAY2023**

The DSMB will review all adverse events (not necessarily serious, unexpected, and study-related) during scheduled DSMB meetings. The Data Coordinating Center will prepare a Summary Report of Adverse Events for the DSMB meetings, classified with the MedDRA coding system.

During these routine meetings of the DSMB, they will review eligibility and recruitment, adverse events, safety analyses, and study data. The DSMB has the ability to use their discretion on suspending enrollment in the trial due to reported adverse events, safety analyses and findings from the study data. The DSMB will be un-blinded to the treatment arm.

Under 21 CFR 312.32(c), the Sponsor is required to notify FDA and all participating investigators in an IND safety report (i.e., 7- or 15-day expedited report) of potentially serious risks from clinical trials or any other source as soon as possible, but no later than 15 calendar days after the Sponsor receives the safety information and determines that the information qualifies for reporting.

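### Expedited reporting does not cover every stopping trigger, and the detailed-report deadline can pass before the site knows of the event

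*Combined protocol and SAP*

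**What the plan says.** **Stopping triggers.** Study Stopping/Discontinuation lists five: any death; a related SAE; severe hypersensitivity in at least 10% of enrolled patients; one hypersensitivity case needing invasive intervention; and "an adverse event that is classified as Severe per protocol that is possibly or probably related to the IP Injection". The last is listed apart from the related-SAE trigger and does not require seriousness. The severity definitions add that a severe event is not necessarily a serious one.

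**24-hour notice.** Two categories carry it. Under Monitoring Serious Adverse Events and IND Safety reports, site staff "will report serious adverse events to the Data Coordinating Center within 24 hours of becoming aware of the event". Under Unanticipated Problems (UP), "The site investigator will report unanticipated problems to the Data Coordinating Center within 24 hours of becoming aware of the event". A UP must be unexpected, related or possibly related to participation, and must suggest a greater risk than was previously known.

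**Other adverse events.** Data Collection Procedures for Adverse Events has them recorded with relatedness, severity and expectedness, and sets no time limit for sending them on. The monitoring section then says: "The DSMB will review all adverse events (not necessarily serious, unexpected, and study-related) during scheduled DSMB meetings". It gives no meeting interval.

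**Detailed reports.** For SAEs, "A detailed completed report will be required to be sent to the Data Coordinating Center within 3 working days of the event". The UP section starts its detailed-report clock at the same point.

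**Notice after a trigger.** The stopping section requires the FDA, DSMB, IRB and Sponsor to be told once enrollment has been suspended. It sets no time limit.

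**The concern.** The fast-reporting categories and the stopping list were drawn up on different criteria. Reporting depends on seriousness, or on unexpectedness together with increased risk. One trigger depends on severity and relatedness alone. Where these diverge, a trigger can be met with no deadline for telling the Data Coordinating Center or the medical monitor.

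Recognition is exposed to the same gap. Relatedness must be judged by an investigator, while the scheduled adverse-event calls are made by the study team, and no time limit is set for grading an event that is not an SAE. The medical monitor's review and sign-off cover SAEs, and the emergency routes for halting enrollment are written for unexpected, study-related SAEs and for UPs. In a Phase I/II trial whose first stated objective is safety, outside oversight should hear promptly of anything the plan itself treats as grounds to stop.

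The second issue is one of workability. A deadline counted from the event, when the site may not yet know of it, can be impossible to meet and would produce protocol deviations that nobody could have prevented.

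**Working it through.** No sample size, power or alpha figure bears on this point, and the plan states no number to reproduce. The check compares the text and then the two clocks.

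**Step 1. Set each trigger against the 24-hour routes.**

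| Trigger | 24-hour route |
|---|---|
| Any death | Yes, as an SAE |
| Related SAE | Yes, as an SAE |
| One hypersensitivity case needing invasive intervention | Probably, as an SAE (medical-judgment clause) or a UP (hypersensitivity is not on the expected list); depends on judgment |
| Severe hypersensitivity in at least 10% of enrolled patients | Individual cases may qualify; no rule covers reaching the threshold (6 patients if 60 are enrolled: 0.10 × 60) |
| Severe, possibly or probably related AE | Only if it is also an SAE or a UP |

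**Step 2. Can the last row fall outside both routes?** An event can be Severe because it interrupts usual daily activity and may need treatment, without meeting any listed SAE criterion. If it is also consistent with the described risks, or does not suggest a greater risk than was known, it is not a UP. Such an event meets a trigger and has no notice deadline.

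**Step 3. Compare the clocks.** Scheduled adverse-event contacts (Patient Study Calendar; Data Collection) are at days 1 and 2 and months 1, 3, 6 and 12. The windows are ±5 hours for day 2, ±1 week for month 1, ±2 weeks for month 3, and ±1 month for months 6 and 12. Assumptions: a month is 30.44 days, and working days are Monday to Friday with no holidays.

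- Nominal gap = later contact − earlier contact.
- Shortest gap = nominal gap − both windows.

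| Interval | Nominal (days) | Shortest (days) |
|---|---|---|
| Day 2 to month 1 | 30.4 − 2 = 28.4 | 28.4 − 0.2 − 7 = 21.2 |
| Month 1 to 3 | 60.9 | 60.9 − 7 − 14 = 39.9 |
| Month 3 to 6 | 91.3 | 91.3 − 14 − 30.4 = 46.9 |
| Month 6 to 12 | 182.6 | about 121.8 |

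Three working days are 3 calendar days for an event on Sunday, Monday or Tuesday, 4 for Saturday, and 5 for Wednesday to Friday. Every gap after the 48-hour call exceeds 5 days, even at its shortest.

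**Step 4. Illustration.** Suppose an SAE occurs on day 5 and the site first hears of it at the month-1 contact, about day 30. The detailed report was due between day 5 + 3 = 8 and day 5 + 5 = 10, which is 20 to 22 days before the site knew. First notice is due on day 31 and can still be met.

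**The case against.** Several points on the other side stand and limit the finding.

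- **Not all Severe events are missed.** A reader might infer that a Severe reaction of a listed type (injection-site pain, swelling or effusion, soreness, bleeding) can never receive expedited notice because it is expected. The expectedness definition does not support that: severity out of line with the described risk can itself make an event unexpected, and the list gives no severity grades. Severe events are also described as usually potentially life-threatening or incapacitating, which overlaps the SAE criteria. What remains is a subset, because a UP must also suggest increased risk and neither overlap is complete.
- **A stopping mechanism exists.** A reader might infer that dosing simply continues until the next DSMB meeting. The stopping section makes the event itself the trigger and does not wait for a meeting. Study drug is given only at the Orthopedic Center, and the site investigator is responsible for evaluating events and ensuring they are reported. Resumption needs FDA approval. What is missing is a deadline for outside notice.
- **The size cannot be put in participants.** It is tempting to calculate the chance of such an event, or the number enrolled during a delay. The documents give neither an event rate nor a DSMB interval, and the first six participants enter one per week with DSMB review before enrollment proceeds. Such figures would rest on assumption alone.
- **The 3-day clock may be loose drafting.** Participants are told to contact the team at any point, and extra calls are allowed. These reduce late discovery but do not rule it out. In each section the two clocks are worded differently, so the text as written sets two starting points.
- **Other documents may fill the gap.** The manual of operations is to detail safety reporting, and the DSMB has a charter. Neither was available. Even if they set timelines, the protocol's own wording should agree with its stopping list.

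**Conclusion.** The point holds in limited form. Of the five stopping triggers, the Severe-and-related one has no assured 24-hour route for events that are neither SAEs nor UPs, and no rule covers reporting when the cumulative hypersensitivity threshold is reached. The gap concerns prompt outside notice and recognition; it is not the absence of a stopping rule. How many events would fall into it cannot be estimated from the documents.

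The clock conflict is plain on the text. For an SAE or UP first learned of at a scheduled contact after the 48-hour call, a deadline of 3 to 5 calendar days from the event can lapse before awareness, given contacts about 28 to 183 days apart. Only the detailed follow-up report is affected, since first notice still runs from awareness. The gap lengths rest on the month length and working-week assumptions stated above, and the conclusion would survive any reasonable change in them.

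Neither issue affects the efficacy analysis. Together they are worth correcting as an inexpensive safety improvement.

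**What to change.** 1. In Monitoring Serious Adverse Events and IND Safety reports, add a sentence to this effect: *Any individual event that meets a criterion under Study Stopping/Discontinuation, and the point at which the cumulative 10% hypersensitivity criterion is reached, will be reported to the Data Coordinating Center and the medical monitor within 24 hours of the site becoming aware, whether or not the event is serious or unexpected. The investigator's severity and relatedness grading will be included or will follow promptly.* Allowing the grading to follow lets a coordinator send the first notice, since coordinators may not assess relatedness.
2. In that section and in Unanticipated Problems (UP), start the detailed-report clock when the site becomes aware of the event, so that both clocks share one starting point.
3. Bring the manual of operations into line and add a flag to the adverse-event form for events that meet a stopping criterion.

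The triggers themselves stay as they are. The cost is the amendment wording, the form change, a few additional expedited reports, and prompt investigator grading of those events.

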**A Phase I/II Randomized, Double-Blinded Standard of Care (Corticosteroid vs Sterile Amniotic Fluid for Osteoarthritis**

**PI: [name].**

**Version: 5.00 dated 23MAY2023**

The DSMB will review all adverse events (not necessarily serious, unexpected, and study-related) during scheduled DSMB meetings. The Data Coordinating Center will prepare a Summary Report of Adverse Events for the DSMB meetings, classified with the MedDRA coding system.

During these routine meetings of the DSMB, they will review eligibility and recruitment, adverse events, safety analyses, and study data. The DSMB has the ability to use their discretion on suspending enrollment in the trial due to reported adverse events, safety analyses and findings from the study data. The DSMB will be un-blinded to the treatment arm.

Under 21 CFR 312.32(c), the Sponsor is required to notify FDA and all participating investigators in an IND safety report (i.e., 7- or 15-day expedited report) of potentially serious risks from clinical trials or any other source as soon as possible, but no later than 15 calendar days after the Sponsor receives the safety information and determines that the information qualifies for reporting.

**Follow-up of Serious, Unexpected and Related Adverse Events**

All serious, unexpected and related adverse events, that are unresolved at the time of the patient's termination from the study, will be followed by the Clinical Center investigators until the events are resolved, subject is lost to follow-up, the adverse event is otherwise explained or has stabilized, or 12 months have passed from the time of last study dose.

